5.6 Prohibited Interventions

No sulfonylurea agents may be administered during the first 4 days of admission. Subsequently, it is preferable that no sulfonylureas be administered through study completion. However, use of sulfonylureas starting beyond Day 4 will not result in study discontinuation.

The use of therapeutic steroids or hypothermia (cooling to below 36 Celsius) is discouraged for treatment of the patient's acute SCI. If the patient requires steroid therapy for the treatment of another condition, this is allowable.

No other investigational drugs may be administered during the study follow-up period. Decisions on whether to withdraw the patient from the study will be made on a case-by-case basis should another investigational drug nevertheless have been administered.

5.7 Interventions Related to Blood Glucose

- **Insulin**

Insulin is not permitted during the period of study drug administration when BG < 120 mg/dL. "Tight" BG control (80 – 110 mg/dL) is not permitted during the period of study drug administration.

- **Supplemental Fluids**

Supplemental fluids are to be standard of care except that during glyburide administration, D5NS or D10NS must be used instead of NS if necessary to maintain BG above 80 mg/dL. Total fluid volume should be consistent with site clinical practice and the clinical status of the subject.

- **Hypoglycemia treatment**

Any BG of < 70 mg/dL must be promptly treated with a bolus of D50W at a volume (ml) of $(100 - \text{BG in mg/dL}) \times 0.4$ as per Juneja et al. 2009 [31]. If supplemental fluids are NS, D5NS should be started. If supplemental fluids are D5NS, D10NS should be substituted. All BG < 70 mg/dL also should preferably be verified by laboratory testing, but repeat point-of-care tests may be used as well. To avoid false readings, blood for the repeat test must be drawn prior to treatment with D50W or switching supplemental fluids.

- **Glyburide Dose Reduction**

Glyburide dosing must be reduced if subject is being administered D5NS or D10NS and (i) there is one confirmed BG < 55 mg/dL; or (ii) there are three confirmed BG < 70 mg/dL within a 12-hour period. If (i) or (ii) above occurs and the subject is on NS, D5NS or D10NS must first be started. If criteria (i) or (ii) are still met, then glyburide dosing should be adjusted to every 8 hours until three consecutive blood glucose readings of >70 are noted. If appropriate levels of BG are not reached within 8 hours of the first dose reduction, the next dose of glyburide should be skipped as an additional dose reduction. Glyburide dosage must only be adjusted based on verified laboratory or repeat point-of-care test values that are taken 15 minutes or more following the last administration of insulin.

- **Glyburide Discontinuation**

The dosing regimen can only be reduced twice; if (i) or (ii) above occurs a third time, glyburide must be discontinued. Glyburide dosage must only be stopped based on verified laboratory test values or, if not available, a repeat point-of-care that are taken 15 minutes or more following the last administration of insulin. When glyburide is stopped as a result of low BG, D50W should be administered by bolus in order to maintain BG > 80 mg/dL. Multiple D50W boluses may be administered, the timing and volume of which are at the discretion of the clinician. BG monitoring is required every 15 (\pm 10) minutes until BG \geq 80 for 3 consecutive readings without bolus glucose supplementation, then hourly (\pm 30 minutes) for the next 6 hours.

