2.2 Glyburide and Signaling Background

Glyburide (also known as Glibenclamide; 5-chloro-N-(4-[N-(cyclohexylcarbamoyl)sulfamoyl]phenethyl)-2-methoxybenzamide) is an anti-diabetic medication in a class of medications known as sulfonylureas. In treating NIDDM, the drug works by inhibiting ATP-sensitive potassium channels in pancreatic beta cells by antagonism of SUR1. This inhibition causes cell membrane depolarization, which causes voltage-dependent calcium channels to open, which in turn causes an increase in intracellular calcium in the beta cell, stimulating insulin release.

The Sur1-Trpm4 channel is selectively expressed in the central nervous system (including the spinal cord) under conditions of ischemia, hypoxia, and trauma [6, 8-10], leading to vasogenic and cytotoxic edema followed by oncotic cell death [11]. With respect to micro vascular endothelial cells, this process leads to the formation of space- occupying edema and secondary hemorrhage. Spinal cord edema and micro hemorrhage formation through this mechanism is a critical secondary injury process that progressively exacerbates mechanical compression, ischemia, and neuronal/glial cell death following trauma [12].

Numerous pharmacokinetic studies of oral glyburide have assessed single-dose administrations in normal subjects and have demonstrated significant absorption within one hour, peak drug levels at about four hours, and low but detectable levels at twenty-four hours. Mean serum levels of glyburide, as reflected by areas under the serum concentration-time curve, increase in proportion to corresponding increases in dose. Multiple-dose studies with glyburide (a widely available oral glyburide formulation) in diabetic patients demonstrate drug level concentration-time curves similar to single-dose studies, indicating no build-up of drug in tissue depots. The decrease of glyburide in the serum of normal healthy individuals is biphasic, the terminal half-life being about 10 hours [34].

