5.8 Days 1-7 (0-168 hours)

- The first dose of glyburide must be administered within 8 hours of injury and stopped after 72 hours. Hard stop rules for glyburide administration are listed below.
- As per recommended standard-of-care guidelines [3], subjects will be admitted to the intensive care unit following initial diagnostic testing where continuous respiratory, cardiac, and hemodynamic monitoring will be undertaken [32]. Maintenance of normal blood oxygenation and a mean arterial blood pressure of 85-90 mmHg will be emphasized in this monitored setting continuously over the first full 7 days following injury.

- The following assessments will be performed through day 7 following injury (during and after study drug regimen):
 - Safety labs: 24 hours (± 12 hours), 48 hours (± 12 hours) 72 hours (± 12 hours) and 96 hours (± 12 hours).
 - Hematology: complete blood count
 - Chemistry: electrolytes (sodium, potassium, chloride, bicarbonate), BUN, creatinine
 - Liver Function Tests: AST, ALT, bilirubin (total and direct), and alkaline phosphatase
 - Blood glucose (BG) monitoring will be hourly (± 30 minutes) for Hours 1-24, every 2 hours (± 30 minutes) for Hours 25-48 and every 4 hours (± 60 minutes) for Hours 49-88. If BG < 70 mg/dL, BG monitoring is required every 15 (± 10 minutes) minutes until BG ≥ 80 for 3 consecutive readings without exogenous bolus glucose supplementation, then hourly (± 30 minutes) for the next 12 hours and every 2 hours (± 30 minutes) thereafter.
 - Continuous bedside cardiac telemetry monitoring from Hour 0 through Hour 72
 - ECG (12-lead) at 4-6 hours, 24 \pm 6 hours, 48 \pm 6 hours and 60-72 hours (from the start of study drug regimen). The ECGs will be read within 12 hours, recorded as clinically significant or non-clinically significant, and signed off on by study team member.
 - Blood sampling for PK prior to dosing, at 4-6 hr (prior to the second study drug administration), 24 \pm 6 hours, 48 \pm 6 hours and 60-72 hours.
 - PK Samples to be drawn as close as possible to ECGs
 - Start time of drug and time of subsequent dosing. Record reason for any missed doses.
 - Concomitant medications and procedures/therapies
 - Review safety and AEs

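### The insulin limit and tight-control ban in section 5.7 end with dosing, about 16 hours before scheduled glucose checks end and with glyburide still present

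*Combined protocol and SAP*

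**What the plan says.** All references are to the combined protocol and SAP.

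- **Insulin (5.7):** "Insulin is not permitted during the period of study drug administration when BG < 120 mg/dL". On tight control: "BG control (80 – 110 mg/dL) is not permitted during the period of study drug administration". The period named in both sentences is not defined.
- **Dosing (5.5, 5.8):** twelve doses, 1.25 mg and then eleven of 0.625 mg at 6-hour intervals. Section 5.8 adds: "The first dose of glyburide must be administered within 8 hours of injury and stopped after 72 hours".
- **BG checks (5.8; calendar footnote c in 5.11):** hourly to Hour 24, every 2 hours to Hour 48, then "every 4 hours (± 60 minutes) for Hours 49-88".
- **Pharmacology (2.2):** single-dose studies in normal subjects show "significant absorption within one hour, peak drug levels at about four hours, and low but detectable levels at twenty-four hours". The terminal half-life is given as about 10 hours.
- **Other sulfonylureas (5.6):** "No sulfonylurea agents may be administered during the first 4 days of admission".
- **Early stops (5.7, 6.4):** "When glyburide is stopped as a result of low BG, D50W should be administered by bolus in order to maintain BG > 80 mg/dL". BG is then checked every 15 minutes until stable and hourly for 6 hours. Neither section mentions insulin after the stop. Section 6.4 also requires stopping for cardiac, hemolytic and liver reasons, with no added dextrose or 15-minute check rule.

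**The concern.** The two rules exist to prevent hypoglycemia from insulin given on top of a sulfonylurea. They are tied to giving the drug, whereas the risk depends on the drug being present. Read literally, a site could start tight control at 80–110 mg/dL, or give insulin at a BG below 120 mg/dL, as soon as the dosing period ends. On schedule that falls in the stretch with the sparsest checks.

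Hypoglycemia is a named safety outcome in section 3.1, and a confirmed BG below 55 mg/dL must be reported as an SAE. In a safety study of 10 patients, one low value after insulin given with glyburide still present would be hard to attribute. It would also have been partly preventable.

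An early stop raises a second question. The rules could lapse at the stop or continue to the planned 72 hours, and the text does not say which.

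**Working it through.** **Clock.** Hours are counted from the first dose, as section 5.8 states for the ECGs. It gives no zero point for the BG hours, so the injury clock is checked in step 4.

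1. **The plan's own figures.** Day 1: 1.25 + 3 × 0.625 = 3.125 mg. Days 2 and 3: 4 × 0.625 = 2.5 mg each. These match Table 2. Dose 12 falls at 11 × 6 = Hour 66, and its 6-hour interval ends at Hour 72.

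2. **Gap between the rules and the end of BG checks.**
   - Rules end at Hour 72: 88 − 72 = 16 h.
   - Rules end at the last dose: 88 − 66 = 22 h.

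3. **Checks in the gap.** They are nominally 4 h apart. With the ±60-minute allowance, two consecutive checks can be 4 + 2 × 1 = 6 h apart. With checks at Hours 52, 56, …, 88, four fall after Hour 72 and six after Hour 66.

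4. **Injury clock.** The first dose may come up to 8 h after injury, so Hour 88 from injury is as early as Hour 80 on the drug clock. The gap is then 80 − 72 = 8 h, or 80 − 66 = 14 h on the last-dose reading. If the 72-hour stop is also counted from injury, the gap is again 88 − 72 = 16 h. It is positive on every reading.

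5. **Drug present in the gap.** From section 2.2, dose 12 peaks at about 66 + 4 = Hour 70 and is detectable to about 66 + 24 = Hour 90. With first-order decay at the 10-hour half-life, ignoring absorption, the share of the Hour-66 amount that remains is 0.5^((t − 66)/10):

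| Hour | Share remaining |
|---|---|
| 72 | 0.5^0.6 = 66% |
| 80 | 0.5^1.4 = 38% |
| 88 | 0.5^2.2 = 22% |

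   These shares are illustrative, because the half-life comes from healthy individuals.

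6. **Early stop, last dose at Hour T.** If the rules lapse at the stop, nothing limits insulin from then on. If they run to Hour 72, cover after the last dose is 72 − T. That is at least 22 h when T ≤ 50 and shorter for later doses; for example, 72 − 62 = 10 h.

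**The case against.** The case against is substantial, and much of it stands.

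- **The period is fairly clear on schedule.** Sections 5.5 and 5.8 point to Hours 0–72. That makes 16 h the main figure and 22 h the weaker reading. It also means the rules cover the peak of dose 12 at about Hour 70. This stands.
- **Detectable does not mean clinically active.** Section 2.2 does not show that the declining level after the last dose lowers glucose enough to need an insulin limit. This stands: the case rests on precaution, not on a demonstrated effect.
- **Limits that end before monitoring can be a coherent design.** A plan may restrict during dosing and only observe during washout. The sulfonylurea ban in 5.6 lasts 4 days from admission but carries no stated glucose rationale, so it is weak support. A reader might infer that the plan contradicts itself; it does not.
- **Existing protection is good.** Dextrose rescue below 70 mg/dL has no time limit. Under 5.8, any BG below 70 mg/dL triggers checks every 15 minutes until stable, then hourly for 12 h, then every 2 h with no stated end. After a stop for another reason, the routine checks continue by study hour. A reader might infer that a low value would go unseen; the documents do not support that.
- **Insulin exposure in the gap is unknown.** A reader might take the 53% hyperglycemic on admission in section 2.0 to mean that about half the patients would be exposed. That figure concerns admission and values of at least 126 mg/dL, and says nothing about insulin below 120 mg/dL three days later. Section 5.7 foresees insulin when it requires verified laboratory values or, "if not available, a repeat point-of-care that are taken 15 minutes or more following the last administration of insulin", but that clause governs decisions made while dosing is still under way.

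What remains is that rescue and checks act after a low value has occurred. The two rules in question help prevent it, and nothing replaces them once they end.

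**Conclusion.** The point holds as a modest preventive gap. On schedule, the insulin limit and tight-control ban most naturally end 16 h before scheduled BG checks do. The range is 8 h (BG hours counted from an injury 8 h before the first dose) to 22 h (rules ending with the last dose). Drug from the last doses is still present and checks are 4-hourly. After an early stop the rules may end at once. Patients stopped for cardiac, hemolytic or liver reasons then have only routine checks and the general rescue rule.

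This rests on the protocol's own schedule and its healthy-subject pharmacology. It does not show that hypoglycemia is likely, and the frequency of insulin use below 120 mg/dL cannot be estimated from the documents. No sample size, test or analysis is affected. The change is worth considering as a cheap improvement; it is not a condition for running the study.

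**What to change.** In section 5.7, for the insulin limit and the tight-control ban, replace the time phrase with: *from the first dose until the end of scheduled BG monitoring (Hour 88), and for at least 22 hours after the last glyburide dose given, including after early discontinuation.* The 22 h is 88 − 66, chosen to match the existing end of monitoring; it is not a pharmacological threshold.

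The cost is a wording change. On schedule, staff apply existing rules for 16 to 22 h longer, and insulin at a BG of 120 mg/dL or above stays allowed. A patient stopped early would stay under the rules to Hour 88. That is 16 h beyond the Hour 72 reading, but longer if the rules are now read as lapsing at the stop.

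Extending BG checks past Hour 88 when the last dose is late is optional. A dose 12 given 2.5 h late would take the rules to 66 + 2.5 + 22 = Hour 90.5. A last dose at the 72-hour limit would take them to 72 + 22 = Hour 94, which means one or two more 4-hourly checks.

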5.5 Study Drug Description, Dose, and Administration

Enrolled patients will receive 12 doses of glyburide starting within 8 hours of SCI. The dosing regimen involves an initial dose of 1.25 mg followed by eleven consecutive doses of 0.625 mg every 6 hours. The total daily dose of glyburide on Day 1, Day 2 and Day 3 will be 3.125 mg, 2.5 mg, and 2.5 mg respectively (see Table 2).

Table 2: Study Dosing

	Day 1	Day 2	Day 3
Total Dose	3.125 mg	2.5 mg	2.5 mg
	First dose of 1.25 mg then 0.625 mg every 6 hours	0.625 mg every 6 hours	0.625 mg every 6 hours

This injury-to-drug timeframe will apply to patients managed non-operatively as well as to patients undergoing surgery (likely a majority of patients in the trial). Drug administration should not be stopped as the standard of care diagnostic studies and treatment is provided, including if the patient is transferred to the OR for decompression and stabilization. Hard stop rules for glyburide administration are listed below.

In the event a dose of glyburide is missed (beyond 2.5 hours from the expected administration time), the next dose should be administered at 1.25 mg followed by the usual 0.625 mg dose for subsequent administrations. If the missed dose is acknowledged within 2.5 hours of the expected administration time the dose should be given and the deviation noted.

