Glyburide must be discontinued if the dose has already been reduced in accordance with the defined guidelines and following the reduction (i) there is one lab or repeat point-of-care confirmed BG < 55 mg/dL; OR (ii) there are three lab or repeat point-of-care confirmed BG < 70 mg/dL within a 12-hour period. When glyburide is stopped as a result of BG, D50W or an equivalent amount of dextrose using D5W, D10W, D25W, or D70W (or other concentration) should be administered by bolus in order to maintain BG > 80 mg/dL. Multiple such boluses may be administered, the timing and volume of which are at the discretion of the clinician. BG monitoring is required every 15 (\pm 10) minutes until BG \geq 80 for 3 consecutive readings without bolus glucose supplementation, then hourly (\pm 30 minutes) for the next 6 hours.

- Cardiac

Glyburide must be halted if:

1. A life threatening cardiac-related SAE occurs, whether or not believed by the clinician to be related to glyburide, and/or
 2. Subject experiences QTc of > 550 ms (Bazett's formula) for 15 minutes, whether or not believed by the clinician to be related to glyburide. Before a decision to stop glyburide is made, ECG leads must be repositioned and must be confirmed to be in the correct position, following which the ECG must be repeated in order to confirm QTc > 550 ms.
- Hemolytic Anemia
Glyburide must be discontinued if hemolytic anemia, which in the judgment of the investigator is severe, is detected. In the event of hemolytic anemia, a G6PD deficiency test should be performed following resolution of anemia. This test generally has a multi-day turnaround and will be used for information purposes only.
 - Liver Function
Glyburide must be discontinued if ALT raises to greater than 8-fold the upper limit of normal. Glyburide must be discontinued if the subject develops cholestatic jaundice or hepatitis.

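### Section 5.7 can release the 8-hour glyburide interval on readings raised by the required D50W bolus, before any dose has been delayed

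*Combined protocol and SAP*

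**What the plan says.** Section 5.7 (Glyburide Dose Reduction) says that dosing must be reduced in a patient on D5NS or D10NS after either of two triggers: one confirmed glucose below 55 mg/dL, or three confirmed values below 70 in 12 hours. A patient on plain saline is first moved to dextrose fluid and is reduced if a criterion is still met. The first reduction is that "glyburide dosing should be adjusted to every 8 hours until three consecutive blood glucose readings of >70 are noted". Return to 6-hour dosing is implied by the word until; it is not stated.

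The next sentence holds the paragraph's only other time limit on the reduction: if glucose has not reached appropriate levels 8 hours after the first reduction, a dose is skipped. On which values may be used, the section says "Glyburide dosage must only be adjusted based on verified laboratory or repeat point-of-care test values" and excludes values within 15 minutes of insulin. It does not mention values after dextrose.

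Two other provisions treat glucose readings more carefully:

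- Section 5.7 (Hypoglycemia treatment): "Any BG of < 70 mg/dL must be promptly treated with a bolus of D50W", and for confirming a low value, "To avoid false readings, blood for the repeat test must be drawn prior to treatment with D50W or switching supplemental fluids".
- Section 5.8: after a value below 70, "BG monitoring is required every 15 (± 10 minutes) minutes until BG ≥ 80 for 3 consecutive readings without exogenous bolus glucose supplementation", followed by hourly checks for 12 hours.

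**The concern.** The reduction is compulsory, but its end point can be met by the rescue treatment alone. The bolus is sized on the shortfall from 100 mg/dL, which is 30 mg/dL above the release threshold of 70. A reading above 70 soon after the bolus is what the treatment is meant to produce, and it says little about whether the next glyburide dose is safe on schedule. With checks every 15 minutes, three such readings can accumulate quickly.

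The protocol applies a stricter standard to a lesser decision. Stepping down the frequency of glucose checks needs three readings of at least 80 without bolus glucose. Ending the longer dosing interval needs three readings above 70, with no condition on bolus glucose. A patient who reads 71 three times after D50W is released from the 8-hour interval while still needing 15-minute checks.

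Safety is a primary objective, and Table 1 in Section 3.1 makes a confirmed value below 55 an SAE. The patients concerned have gone low, or stayed low, despite dextrose fluids. The stopping rules in 5.7 and 6.4 act only after a further low.

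**Working it through.** **Inputs.** Dose interval 6 h = 360 min, 12 doses, first 1.25 mg and then 0.625 mg (5.5). Checks every 15 ± 10 min after a value below 70, so gaps of 5, 15 or 25 min (5.8). Release at three consecutive readings above 70, and D50W volume (100 − BG) × 0.4 mL (5.7). Missed-dose limit 2.5 h (5.5). Dosing stops after 72 h (5.8).

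**The plan's own dose figures.** Day 1: 1.25 + 3 × 0.625 = 3.125 mg. Days 2 and 3: 4 × 0.625 = 2.5 mg. Both agree with Table 2. A full day at 8-hour intervals would give 3 × 0.625 = 1.875 mg, which is 25% less than 2.5 mg. If the reduction lapses before the next dose, the decrease is zero.

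**Bolus.** At BG 54: 46 × 0.4 = 18.4 mL. At BG 69: 31 × 0.4 = 12.4 mL.

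**Time to release.** Assume that the first three readings after the trigger all exceed 70. Release then comes 3 × gap after the trigger. The text does not say whether the verification requirement covers release. If it does, and each retest is taken at the next check, release comes 6 × gap after the trigger.

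**Which triggers lapse.** The release clock starts at the trigger, and the dose clock starts at the last dose. The next dose stays at 6 h if trigger time + release time is less than 360 min. The cut-off is therefore 360 − release time.

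| Gap between checks | Release, no retest | Trigger must precede | Share of 6 h | Release, each retested | Trigger must precede | Share of 6 h |
|---|---|---|---|---|---|---|
| 5 min | 15 min | 345 min | 95.8% | 30 min | 330 min | 91.7% |
| 15 min | 45 min | 315 min (5 h 15 min) | 87.5% | 90 min | 270 min | 75.0% |
| 25 min | 75 min | 285 min | 79.2% | 150 min | 210 min | 58.3% |

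These are shares of the dosing interval under immediate recovery. They are not probabilities that a reduction lapses.

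**Example.** Section 2.2 puts peak drug level at about four hours. For a trigger at 4 h (240 min):

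- Nominal checks: release at 240 + 45 = 285 min, so the 6-hour dose is unmoved.
- Nominal checks with retests: 240 + 90 = 330 min, again unmoved.
- Slowest check spacing with retests: 240 + 150 = 390 min, so the 8-hour interval is still in force at 360 min and the dose is delayed.

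**The case against.** The best defence is that the paragraph opens by requiring a reduction, and a reading under which no dose moves reduces nothing. On that view, dosing every 8 hours means at least one full 8-hour interval, and the 8-hour skip clause suggests that the response is judged over such a window. This is a reasonable reading, and some sites will follow it. The text does not state it, though, and the skip clause escalates when recovery fails; it sets no minimum duration.

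The backstops are also real. Besides the skipped dose, there are D50W, D5NS or D10NS, and 15-minute checks that continue until three bolus-free readings of at least 80, whatever happens to the dosing interval. Discontinuation follows further triggers. A 2-hour delay also changes exposure little: with the terminal half-life of about 10 hours that Section 2.2 gives for healthy people, 0.5^(2/10) = 0.87 of the residual drug remains. All of this stands, and it limits the severity.

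Three stronger readings go further than the documents allow:

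- **That 150 minutes is the slowest possible release, so the reduction always lapses in time.** Any reading of 70 or below restarts the count, so there is no upper limit. Release and dosing also run on different clocks, so a late trigger does delay a dose.
- **That these patients are left unprotected.** The backstops above remain in force.
- **That the stopping rules misfire because a reduction that delayed no dose may not count.** Section 6.4 says "Glyburide must be discontinued if the dose has already been reduced in accordance with the defined guidelines and following the reduction". A reduction ordered and released under 5.7 fits those words, so the next trigger stops the drug, which is the protective direction. Section 5.7 differs ("The dosing regimen can only be reduced twice; if (i) or (ii) above occurs a third time, glyburide must be discontinued"), but how many reductions are allowed is a separate matter.

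**Conclusion.** The gap is real and minor. Followed as written, the 8-hour interval can end on readings raised by the bolus before any dose has moved. At nominal check spacing this can happen for any trigger earlier than about 5 h 15 min after the last dose, or 4 h 30 min if each reading is retested. Both figures assume that the first three readings all exceed 70.

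How often this would occur cannot be estimated, because the documents give no data on glucose recovery after the bolus. A late trigger, slow recovery, or a site that takes the rule to mean one full interval would still produce a delay. The stake per event is one 0.625 mg dose given 2 hours earlier than intended, in at most 10 closely monitored patients. No endpoint or analysis is shown to change.

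**What to change.** Add one or two sentences to Section 5.7. They should say that the 8-hour interval applies to at least the next scheduled dose after the trigger, and that only readings without bolus glucose supplementation, as in 5.8, count toward release. The threshold of 70 can stay. The same edit could settle whether the verification requirement applies to release.

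The cost is a delay of 8 − 6 = 2 h per affected dose. That is inside the 2.5-hour limit in 5.5, so it does not set off the rule that when "a dose of glyburide is missed (beyond 2.5 hours from the expected administration time), the next dose should be administered at 1.25 mg".

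The 12th dose normally falls at 11 × 6 = 66 h. One, two or three 8-hour intervals move it to 68, 70 or 72 h. A fourth would put it at 74 h, past the 72-hour stop. So it would be wrong to infer that no dose can ever be lost: the timing holds for up to three such intervals, with the third exactly at the limit. The amended text should say that dosing still ends at 72 hours in that case.

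### For a patient already on dextrose fluids at the first hypoglycemia trigger, sections 5.7 and 6.4 set different mandatory stop points for glyburide

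*Combined protocol and SAP*

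**What the plan says.** Section 5.7 sets out a stepwise response to low BG.

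- **Fluids.** Any BG below 70 mg/dL is treated with a dextrose bolus and a fluid change: "If supplemental fluids are NS, D5NS should be started".
- **Dose reduction.** "Glyburide dosing must be reduced if subject is being administered D5NS or D10NS" and either trigger is met: (i) one confirmed BG below 55 mg/dL, or (ii) three confirmed values below 70 mg/dL in 12 hours. For a patient still on NS, the fluid step comes first: "If (i) or (ii) above occurs and the subject is on NS, D5NS or D10NS must first be started".
- **Form of the reduction.** On a reduction, "glyburide dosing should be adjusted to every 8 hours until three consecutive blood glucose readings of >70 are noted". If BG has not recovered within 8 hours of that first reduction, "the next dose of glyburide should be skipped as an additional dose reduction".
- **Stop.** "The dosing regimen can only be reduced twice; if (i) or (ii) above occurs a third time, glyburide must be discontinued".

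Section 6.4 (Criteria for Intervention Discontinuation, Blood Glucose) repeats triggers (i) and (ii) with the same thresholds, but its stop reads: "Glyburide must be discontinued if the dose has already been reduced in accordance with the defined guidelines and following the reduction" either trigger occurs. It mentions no second permitted reduction.

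Sections 5.5 and 5.8 each say that the hard stop rules for the drug appear later in the document. Neither says which section governs if 5.7 and 6.4 differ.

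**The concern.** Both stop rules are mandatory and use the same glucose thresholds, but they count different things. Section 5.7 counts occurrences of the trigger, and section 6.4 asks whether a reduction has already been made. On at least one ordinary path the two counts give different answers to the same bedside question: may the next dose be given?

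Hypoglycemia is a named safety outcome under the primary objectives (3.1), and up to ten centers may take part (2.0). A site working from 5.7 can redose after a repeat confirmed low and so breach 6.4, while a site working from 6.4 stops. The same event would then be handled differently across sites, on the toxicity that the drug is best known for.

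**Working it through.** The protocol gives no figure to reproduce here. The check steps one patient through successive triggers, then sizes the dose at issue.

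**Step 1. Stop points by path**

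| Path | Trigger | 5.7 | 6.4 | Agree? |
|---|---|---|---|---|
| On dextrose at the first trigger | 1st | First reduction | Not yet engaged | Yes |
| | 2nd | Second reduction still available; no mandatory stop | Stop | **No** |
| | 3rd | Stop | Stop already required | – |
| On NS at the first trigger, which is counted | 1st | Fluid change only | Not yet engaged | Yes |
| | 2nd | First reduction | Not yet engaged | Yes |
| | 3rd | Stop | Stop | Yes |

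The number of earlier reductions does not by itself define the conflict. At the third trigger on the NS path the patient has also had exactly one reduction, and the sections agree. What matters is whether a trigger was used up on a fluid change.

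**Step 2. Which path is likely?** Under 5.7 any BG below 70 on NS already calls for D5NS. A patient who reaches trigger (ii), or trigger (i) after an earlier low, should therefore be on dextrose when the trigger is met. The NS path is left mainly to a patient whose first low is already below 55.

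**Step 3. Dose at issue**

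Inputs: a first dose of 1.25 mg, then eleven doses of 0.625 mg every 6 hours (5.5); treatment ends at 72 hours (5.8).

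- Planned course: 1.25 + 11 × 0.625 = 8.125 mg, given at hours 0, 6, …, 66.
- Recurrence at hour 24, maximum under 5.7: doses at 30, 36, 42, 48, 54, 60 and 66. That is 7 × 0.625 = 4.375 mg, and 4.375 / 8.125 = 53.8%.
- Recurrence at hour 48, maximum under 5.7: doses at 54, 60 and 66. That is 3 × 0.625 = 1.875 mg, and 1.875 / 8.125 = 23.1%.
- Minimum under 5.7 in both cases: 0 mg, if a third trigger follows before the next dose.
- Under 6.4 in both cases: 0 mg.

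The maximum takes the second reduction to be another spell of 8-hourly dosing, which ends after three readings above 70. After a low, "BG monitoring is required every 15 (± 10 minutes) minutes until BG ≥ 80 for 3 consecutive readings", so three such readings can arrive in about 3 × 15 = 45 minutes, before the next 6-hourly dose is due. In that case no dose is lost. Section 5.7 does not spell out what form the second reduction takes when it answers a recurrence rather than a failure to recover. If it is one skipped dose, the maximum falls to 6 × 0.625 = 3.75 mg (46.2%) at hour 24 and 2 × 0.625 = 1.25 mg (15.4%) at hour 48.

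These figures assume a dose given at the hour of the trigger and none at or after hour 72.

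**The case against.** **The sections can be reconciled.** The reference in 6.4 to reduction under the defined guidelines could mean that both reductions in 5.7 have been used. This is possible, but 6.4 never mentions a second reduction, and its wording is satisfied by one. The sections also differ on the evidence needed to stop: 5.7 wants a laboratory value, with a repeat point-of-care test only if none is available, while 6.4 accepts either. That suggests 6.4 is not simply a restatement of 5.7.

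**The text points to 6.4.** Section 5.8 follows 5.7, so its reference to hard stop rules further on leads to 6.4. This stands as a reason to prefer 6.4. It is not a precedence clause and does not cancel the explicit allowance of two reductions in 5.7.

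**A site can satisfy both.** Stopping at the second trigger breaches neither section. True, but 5.7 does not tell the site to do so.

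**The practical impact is small.** This largely stands. Section 2.2 reports phase 1 discontinuations for persistent hypoglycemia only at 6 and 10 mg/day, above the 2.5 to 3.125 mg/day used here, and no new safety concerns in 93 stroke patients at 3 mg/day. Section 2.0 does describe the few treatment-related serious events at 3 mg/day as limited to hypoglycemia, without a count.

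**Stronger readings that the documents do not support.** A reader might infer that the rules conflict whenever exactly one reduction has been made; the NS path shows otherwise. A reader might infer that 5.7 guarantees substantial further dosing; its lower bound is zero. A reader might also think it open whether a skipped dose uses up a reduction; 5.7 already names it as an additional reduction after the first, so it is the second.

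**Conclusion.** The point holds for a patient already on D5NS or D10NS at the first trigger: 6.4 requires a stop at the first trigger after a reduction, and 5.7 only at the third occurrence. It does not hold on the NS path when the NS trigger is counted as an occurrence.

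The difference is 0 to 4.375 mg of further drug after a recurrence at hour 24 and 0 to 1.875 mg at hour 48, under the assumptions stated with the arithmetic. How often patients reach this state cannot be derived from the documents; with 10 patients (4.2) at this dose it is probably rare.

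A reader might infer that patients are left unprotected or that the safety results would be distorted. Neither follows. Dextrose boluses and fluids (5.7), 15-minute checks after a low (5.8), reporting of a confirmed BG below 55 as a serious event (3.1, Table 1) and committee review after every third patient (8.0) apply under either rule. The triggering low is recorded either way, so no planned estimate changes. This is a wording conflict in a mandatory safety rule, worth fixing because the fix is cheap.

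**What to change.** Write one stop rule and put it in both 5.7 and 6.4.

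- **Default:** adopt 6.4. Discontinue glyburide if trigger (i) or (ii) recurs after any dose reduction, and delete the sentence in 5.7 that allows two reductions and stops on the third occurrence. This is the safer default because stopping at that point breaches neither section as they now stand.
- **Alternative:** if the sponsor and the DSMC prefer two reductions, amend 6.4 to say so. The documents do not show which limit is better at this dose, so the choice is theirs.
- **In either case:** state that a trigger on NS answered only by a fluid change is not a dose reduction. The skipped dose needs no new rule.

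The cost is a wording amendment, IRB approval (9.1 requires it for modifications) and a notice to sites, with no added procedures or patients. Under the default, the few subjects who reach this state may lose their remaining doses, up to 54% of the course in the hour-24 example, and some pharmacokinetic data with them.
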